11.5 Risk-Benefit Rationale

Consensus statements and evidence-based systematic reviews have been developed to guide the use of infusion therapy with morphine for chronic intractable pain. Both the SynchroMed II infusion system and PFMS are commercially available, with a positive risk-benefit ratio established for each.

12. Adverse Events and Device Deficiencies

12.1 Definitions / Classifications

Any adverse event (AE) meeting the definition of systemic opioid weaning-related, device-related, IT drug-related, and procedure-related, all serious adverse events and deaths (regardless of relatedness) for all subjects from Baseline to the 6-Month Visit, and device deficiencies (DD) for all subjects from Implant to the 6-Month Visit will be collected. All anticipated AEs and adverse device effects are the same as those foreseeable risks listed in Section 11.1.

This post-market study is not within the scope of ISO 14155:2011 but will use AE definitions according to ISO 14155:2011 for consistency in reporting. Each adverse event is classified according to ISO 14155:2011. Adverse events and device deficiencies are defined below in Table 4 as follows:

Table 4: Adverse Event and Device Deficiency Definitions

Term	Definition
Adverse Event (AE): (ISO 14155:2011 3.2)	Any untoward medical occurrence, unintended disease or injury, or untoward clinical signs (including abnormal laboratory findings) in subjects,

Embrace TDD Clinical Investigation Plan

MDT18026

Version 3.0

Page 51 of 74

Form

Medtronic

Term	Definition
	
users or other persons, whether or not related to the investigational medical device.
 
NOTE 1: This definition includes events related to the investigational medical device or the comparator.
 
NOTE 2: This definition includes events related to the procedures involved.
 
NOTE 3: For users or other persons, this definition is restricted to events related to investigational medical devices.

Adverse Device Effect (ADE): (ISO 14155:2011 3.1)	
Adverse event related to the use of an investigational medical device.
 
NOTE 1: This definition includes adverse events resulting from insufficient or inadequate instructions for use, deployment, implantation, installation, or operation, or any malfunction of the investigational medical device.
 
NOTE 2: This definition includes any event resulting from use error or from intentional misuse of the investigational medical device.

Device Deficiency (DD): (ISO 14155:2011 3.15)	
Inadequacy of a medical device with respect to its identity, quality, durability, reliability, safety or performance.
 
NOTE: Device deficiencies include malfunctions, use errors, and inadequate labeling.

Malfunction: (ISO 14155:2011 3.27)	
Failure of an investigational medical device to perform in accordance with its intended purpose when used in accordance with the instructions for use or (CIP).

Use Error: (ISO 14155:2011 3.43)	
Act or omission of an act that results in a different medical device response than intended by the manufacturer or expected by the user.
 
NOTE 1: Use error includes slips, lapses, and mistakes.
 
NOTE 2: An unexpected physiological response of the subject does not in itself constitute a use error.

Term	Seriousness
Serious Adverse Event (SAE): (ISO 14155:2011 3.37)	
Adverse event that
 
 a) led to death, b) led to serious deterioration in the health of the subject, that either resulted in 
 1) a life-threatening illness or injury, or 2) a permanent impairment of a body structure or a body function, or 3) in-patient or prolonged hospitalization, or 4) medical or surgical intervention to prevent life-threatening illness or injury or permanent impairment to a body structure or a body function, c) led to fetal distress, fetal death or a congenital abnormality or birth defect. 
NOTE: Planned hospitalization for a pre-existing condition, or a procedure required by the CIP, without serious deterioration in health, is not considered a serious adverse event.

Term	Definition
Serious Adverse Device Effect (SADE): (ISO 14155:2011 3.36)	Adverse device effect that has resulted in any of the consequences characteristic of a serious adverse event
Term	Relatedness
Systemic Opioid Weaning-Related	An adverse event related to the systemic opioid weaning process (i.e. opioid-related withdrawal symptoms)
Device-Related	An adverse event that results from the presence or performance (intended or otherwise) of the SynchroMed II infusion system.
IT Drug-Related	Event related to the IT drug delivered by the device. Normally IT drug-related events resolve when the device is turned off or reprogrammed, or the drug is removed from the pump. This category should not include events that resulted from a malfunction of the device (i.e. hardware-related events).
Procedure-Related	An adverse event that occurs due to any procedure related to the IT trial, implant, pump refills, programming, or surgical modification of the system.

12.2 Reporting of Adverse Events

Any AE meeting the definition of systemic opioid weaning-related, device-related (i.e. SynchroMed II infusion system), IT drug-related, and procedure-related (i.e. IT trial, implant or pump refill/reprogramming, system modification), and all serious adverse events and deaths (regardless of relatedness), for all subjects from the Baseline Visit through study exit will be collected.

It is the responsibility of the investigator to identify the occurrence of any reportable adverse events and to ensure all required information is accurately recorded in the subject's medical record and reported to Medtronic on an event eCRF. IRB reporting must be completed in accordance with the policies of the governing IRB. Refer to the eCRF for the information to be reported for each AE.

For AEs that require immediate reporting, initial reporting to Medtronic may be done by phone, fax, or e-mail, or on the eCRF by completing as much information as is available. The AE eCRF must be completed as soon as possible.

In case the investigator requires information from the sponsor in an emergency, the investigator can contact Medtronic using the contact details provided in the synopsis and Section 12.5.

The clinical course of each AE must be followed until the adverse event is resolved, the subject is in a stable condition, or until the subject discontinues from the study. "Ongoing" AEs must be assessed at each study visit. The AE eCRF should be updated when there is a change to the information provided on the form (e.g. change in intervention, outcome, relatedness, etc.).

At the last study visit, the investigator will instruct the subject to provide an update on the status of any ongoing events and report any AE they believe may be related to participation in the study.

12.3 Non-Reportable Events

Examples of events that are not reportable as adverse events for this study include:

- Inability to successfully perform a procedure, unless injury occurs
- A documented pre-existing condition unless there is a worsening of the nature, severity, duration or frequency of that condition if it meets the defined criteria for a reportable adverse event (i.e. systemic opioid weaning, device, IT drug and/or procedure-related)

Table 5 provides a list of common expected surgical AEs. An expected surgical event will not be considered reportable unless it worsens or is present outside the stated timeframe post-procedure.

Table 5: Expected Surgical Adverse Events and Durations

Event Description	Timeframe After Surgical Procedure
Low-grade fever (< 100° or <37.8° C)	48 hours
Anesthesia-related nausea/vomiting	24 hours
Mild to moderate bruising/ecchymosis	7 days
Pocket site / incisional pain	14 days
Seroma	72 hours
Sleep problems (insomnia)	72 hours

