10.18 Assessment of Safety

Subjects will be assessed from enrollment through the end of the study for AEs related to the following:

- Systemic opioid weaning

- Device
- IT drug
- Procedure

In addition, all SAEs (regardless of relatedness) and device deficiencies reported during the study will be collected. All subject deaths (regardless of relatedness) must be reported to Medtronic according to Section 12.6.

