7.10 Safety Evaluation

The safety evaluation will characterize all systemic opioid weaning-related, device-related, IT drug-related, and procedure-related adverse events (AEs), all serious adverse events (SAEs) (regardless of relatedness), and device deficiencies (DD) for all subjects from enrollment until the subject exits.

Adverse events and device deficiencies will be coded and summarized using the most recent version of Medical Dictionary for Regulatory Affairs (MedDRA).

The adverse events will also be categorized by relationship to systemic opioid weaning-related, device-related, IT drug-related, and procedure-related adverse events. The CEC adjudicated relatedness will be used for summary tables in the final report. Any differences between CEC adjudication and investigator reporting will be noted in the final report.

Adverse events will be presented in summary tables displaying the number of serious events, the number of events, and the number and percentage of subjects with one or more events. A summary of all adverse events by System Organ Class (SOC) and Preferred Term (PT) will also be provided.

Device deficiencies will be presented in summary tables displaying the number of deficiencies, and the number and percentage of subjects with device deficiencies.

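### Protocol 12.3 omits seriousness from its test for reporting a worsened pre-existing condition, in conflict with the rule in 10.18, 12.1, 12.2 and SAP 7.10 that every SAE is collected whatever its cause

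*Protocol*

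**What the plan says.** Protocol 12.3 opens its list with "Examples of events that are not reportable as adverse events for this study include". The second item is a documented pre-existing condition. It becomes reportable only if it worsens, and then only "if it meets the defined criteria for a reportable adverse event (i.e. systemic opioid weaning, device, IT drug and/or procedure-related"). The item has no time limit and is separate from the surgical-event windows in Table 5.

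The collection rule elsewhere has no relatedness condition for serious events:

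- Protocol 10.18, after listing the four relatedness classes: "In addition, all SAEs (regardless of relatedness) and device deficiencies reported during the study will be collected".
- Protocol 12.1: "all serious adverse events and deaths (regardless of relatedness) for all subjects from Baseline to the 6-Month Visit".
- Protocol 12.2: "all serious adverse events and deaths (regardless of relatedness), for all subjects from the Baseline Visit through study exit will be collected".
- SAP 7.10: the evaluation covers "all serious adverse events (SAEs) (regardless of relatedness), and device deficiencies (DD) for all subjects from enrollment until the subject exits".

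The note to the SAE definition in Table 4 (Protocol 12.1) deals with pre-existing conditions directly. It says that planned hospitalization for one, or a procedure the protocol requires, "without serious deterioration in health, is not considered a serious adverse event".

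**The concern.** The protocol describes a reportable event in two ways. In 10.18, 12.1 and 12.2 there are two routes in: one of the four relatedness classes, or seriousness. The parenthesis in 12.3 gives only the first. It is introduced by i.e., which restates a definition and does not offer examples.

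The exposed event is narrow: a non-fatal serious worsening of a condition documented before the study, judged by the investigator to be unrelated to weaning, device, drug or procedure. An unplanned admission for a long-standing heart or lung condition would be a case. It must be collected under 12.2, but on a literal reading of 12.3 it is not reportable.

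What is at stake is the completeness of the SAE tables. Characterizing all SAEs regardless of relatedness is a stated study objective, and relatedness is meant to be settled by a committee independent of the investigators. If the 12.3 wording were followed literally, the investigator's own judgement of unrelatedness could keep a serious event from that committee.

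**Working it through.** The plan gives no figure on this point, so the check is a comparison of texts, followed by tracing what happens to one event.

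**Step 1: the two rules side by side**

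| Event | 10.18, 12.1, 12.2, SAP 7.10 | 12.3 parenthesis, read literally |
|---|---|---|
| Related worsening, serious or not | Collected | Reportable |
| Unrelated, non-serious worsening | Not collected | Not reportable |
| Unrelated, serious, fatal worsening | Collected; death also notified under 12.6 | Captured in any case by the separate death rule |
| Unrelated, serious, non-fatal worsening | Collected | Not reportable |

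Only the last row conflicts.

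**Step 2: does the SAE definition remove that row?** No. The Table 4 note exempts planned hospitalization only when there is no serious deterioration. A serious deterioration of a pre-existing condition therefore remains an SAE.

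**Step 3: where could an omitted event be recovered?**

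1. Entry: 12.2 makes the investigator responsible for identifying reportable events, so the filter acts before any form exists.
2. Adjudication: under section 13 the CEC classifies reportable events. An unentered event does not reach it by that route.
3. Last visit: 12.2 has the subject update ongoing events and report any that the subject believes may be related to participation. That does not prompt for unrelated ones.
4. Monitoring: 16.1 gives monitors direct access to hospital and clinic charts and provides for source data verification. This could find an unentered admission. How much is verified is set in a monitoring plan outside these documents.
5. Analysis: SAP 7.10 tabulates the adverse events in the database, so it cannot restore an event missing from it.

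**Step 4: direction and unit of effect.** Omission can only reduce the number of serious events. It reduces the percentage of subjects with an SAE only when the subject has no other reported SAE. SAP 7.1.3 uses all enrolled subjects for safety, and 93 were enrolled, so each such subject would move the percentage by 1/93 = 0.0108, about 1.1 percentage points. How many such subjects there are, if any, cannot be obtained from the documents.

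**The case against.** The best defence is that 12.3 refers to defined criteria for a reportable event, and those criteria are set out in 12.1 and 12.2, where all SAEs are included. The unconditional SAE rule appears in nine places: the synopsis, Protocol 5.1.4, 10.18, 12.1, 12.2 and 14.6, and SAP 4.4, 5.2.2 and 7.10. The 12.3 list is offered only as examples, and 10.18 presents SAE collection as an addition to the four classes. On this view the parenthesis is an incomplete restatement, and a site that left out an SAE would be breaching 12.2.

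Much of this stands. It is very probably what the sponsor meant, and many sites will have read it so. It does not remove the inconsistency: the parenthesis restates the criteria and drops one of them, 12.3 is the more specific text for pre-existing conditions, and no rule says which section prevails.

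It is also fair that nothing in the analysis plan is wrong. SAP 7.10 has the correct scope, safety is descriptive, and the primary and secondary objectives are not affected.

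A reader might go further and infer that serious events have been lost, that nothing could recover them, or that a number can be attached by applying an assumed rate to the 93 enrolled subjects. The documents support none of these. They show no omitted event and give no SAE rate. Source data verification is a real route to recovery. A rate applied to all 93 would assume that every site omits every such event and that all subjects have full follow-up, although the plan assumes 33% attrition before implant and a further 25% before the 6-Month Visit.

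**Conclusion.** The inconsistency is real, and it lies in a reporting instruction, not in an analysis choice. Read literally, 12.3 excludes non-fatal serious worsenings of pre-existing conditions that the investigator judges unrelated, while 10.18, 12.1, 12.2 and SAP 7.10 require them. Deaths and all related events are unaffected.

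Any effect would understate the SAE results, and this single-arm study has no comparator in which it could cancel. Its size is unknown and may be zero: it depends on how sites read the parenthesis, how often such events occurred, and how many monitoring found. The conclusion rests on the conflict of texts alone. It is worth correcting because the correction is cheap and completeness of SAEs is a stated objective.

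**What to change.** 1. Reword the 12.3 parenthesis to agree with 12.1 and 12.2, for example: (that is, any serious event whatever its cause, or any event related to opioid weaning, the device, the IT drug or a procedure).
2. Add a sentence that nothing in 12.3 exempts an event meeting the SAE definition in Table 4.
3. Tell sites by memo.
4. Because all 93 subjects were already enrolled when version 3.0 was written, new wording alone does not reach past events. At the interim and closure monitoring visits already planned under 16.1, ask each site whether any hospitalization for a pre-existing condition was left unentered. One question per site is proportionate; without evidence of misreading, a separate retrospective audit is not warranted.

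The SAP needs no change. The cost is a line or two in the protocol, a memo, one added monitoring question, perhaps a few more SAE forms and CEC adjudications, and possibly a slightly higher reported SAE rate.

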12.4 Reporting of Device Deficiencies

Device Deficiency (DD) information will be collected for all subjects from the Implant Visit through the 6-Month Visit and reported to Medtronic on a DD CRF, one for each DD. At the last study visit, the investigator will instruct the subject to provide an update on the status of any ongoing events and report any issue with the device they believe may be related to participation in the study.

12.6 Subject Death

The investigator must notify Medtronic immediately and the IRB (as required), after learning of a subject's death (regardless of relatedness). The death should be reported to Medtronic on the event eCRF as soon as possible. The investigator should also attempt to determine, as conclusively as possible, whether such deaths are related to the systemic opioid weaning, device, IT drug, or procedure.

If it is determined that the cause of death was related to systemic opioid weaning, device, IT drug, or procedure:

- A copy of an autopsy report should be provided to Medtronic, if an autopsy is performed
- Medtronic requests that all device system components that were being used at the time of the death be returned to Medtronic for analysis per Section 7.11
- Requested death certificates and/or source documentation if obtained, should be redacted and sent to Medtronic

If the death occurs at a location remote from the study site, it is the study site's responsibility to make three attempts to retrieve all pertinent information related to the subject's death and submit the investigator's death summary of the known events surrounding the death to Medtronic.

13. Data Review Committees

This study will utilize a Clinical Events Committee (CEC) to adjudicate the relatedness and seriousness classifications of all reportable adverse events.

The CEC may request clarification and/or additional information from the PI who reported the event. If the conclusion of the review differs from the PI's assessment, both opinions will be reported back to the investigator and noted in the final study report. Incidence rates will be tabulated using the final CEC determination.

The CEC will be external to Medtronic and independent of the study investigators. The members will have specialties appropriate to the therapeutic area and meet requirements established in the CEC charter.

14. Statistical Design and Methods

14.1 General Aspects of Analysis

Data analysis will be performed by Medtronic-employed statisticians or designees. A validated statistical software package will be used for the analyses of the study results (e.g. SAS version 9.4 or higher).

The Statistical Analysis Plan (SAP) will be developed prior to data analysis and will include a comprehensive description of the statistical methods and reports to be included in the final study report. Any change to the data analysis methods described in the CIP will require an amendment only if it changes a principal feature of the CIP. Any other change to the data analysis methods described in the CIP, and the justification for making the change, will be described in the clinical study report.

14.1.1 Sample Size Justification

Ninety-three subjects have been enrolled into the study with the intent to achieve approximately 67 implanted subjects and at least 50 evaluable subjects at the 6-Month Visit. The sample size of 50 evaluable subjects was chosen to assure acceptable levels of precision for estimation of the primary objective of Clinical Success and provide adequate power to test the secondary objective related to pain score.

There were no available data in the target population on the primary objective of Clinical Success, nor on the secondary objective of opioid-related side effects score. The secondary objective of pain intensity score is used for sample size calculation. It is hypothesized that the pain intensity score of VAS at the 6-Month Visit is non-inferior to those at Baseline using a non-inferiority approach.

The PASS 11 Non-Inferiority Tests for One Mean was used to calculate the power for pain intensity of VAS with the following assumptions: Sample size = 50, Alpha = 0.025, Non-Inferiority Margin = 1, True Difference = 0, Standard Deviation = 1.9, with Higher Means are Better (one-sided) t-test. A sample size of 50 would achieve 95% power with the above assumptions. This power calculation was performed using a pain scale of 0-10; however, the power calculation is identical to one with a non-inferiority margin of 10 and assuming a standard deviation of 19 on a VAS pain scale of 0-100.

The non-inferiority margin of 10 points (for the VAS of 0-100) was chosen based on a review of pain study literature. Non-inferiority margins between 1 and 1.5 were reported for pain scales of 0-10, including one study in a similar population of chronic non-malignant pain subjects comparing 2 oral opioids that utilized a margin of 1^d. The non-inferiority margin of 1 on a pain scale of 0-10 is equivalent to a non-inferiority margin of 10 on a VAS pain scale of 0-100. The estimated actual difference was assumed to be 0 because the goal is to achieve same or better pain control as compared to Baseline.

A 33% attrition between enrollment and subject implant is assumed and a 25% attrition between Implant and the 6-Month Visit is assumed. Under CIP V2.0, approximately 100 subjects were to be enrolled; 93 subjects have been enrolled into the study with the intent to achieve approximately 67 implanted subjects and 50 evaluable subjects at the 6-Month Visit.

^d Binsfeld H, Szczepanski L, Waechter S, Richarz U, Sabatowski R. A randomized study to demonstrate noninferiority of once-daily OROS® hydromorphone with twice-daily sustained-release oxycodone for moderate to severe chronic noncancer pain, *Pain Pract.* 2010;10(5):404-415.

The 33% attrition between enrollment and subject implant accounts for the subjects who don't meet inclusion and/or exclusion criteria, those who can't follow the weaning process to eliminate systemic opioids, those who don't have a successful IT trial, those who have AE that can no longer be followed in the study, withdrawals, and lost-to-follow-up, etc. The attrition between implant and the 6-Month Visit is conservatively set at 25% to potentially account for the subjects who have adverse events that can no longer be followed in the study, withdrawals, are LTFU, or subjects who can't be effectively managed on morphine monotherapy.

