Approximately 100 subjects will be enrolled into the study to get a minimum of 67 implanted subjects and at least 50 evaluable subjects at the 6-Month Visit. The sample size of 50 evaluable subjects was chosen to assure acceptable levels of precision for estimation of the primary objective of Clinical Success and provide adequate power to test the secondary objective related to pain score.

There were no available data in the target population on the primary objective of Clinical Success, nor on the secondary objective of opioid-related side effects score. The secondary objective of pain intensity score is used for sample size calculation. It is hypothesized that the pain intensity score of VAS at the 6-Month Visit is non-inferior to those at Baseline using a non-inferiority approach.

The PASS 11 Non-Inferiority Tests for One Mean was used to calculate the power for pain intensity of VAS with the following assumptions: Sample size = 50, Alpha = 0.025, Non-Inferiority Margin = 1, True Difference = 0, Standard Deviation = 1.9, with Higher Means are Worse (one-sided) t-test. A sample size of 50 would achieve 95% power with the above assumptions. This power calculation was performed using a pain scale of 0-10; however, the power calculation is identical to one with a non-inferiority margin of 10 and assuming a standard deviation of 19 on a VAS pain scale of 0-100.

The non-inferiority margin of 10 points was chosen based on a review of pain study literature. Non-inferiority margins between 1 and 1.5 were reported for pain scales of 0-10, including one study in a similar population of chronic non-malignant pain subjects comparing 2 oral opioids that utilized a margin of 1.¹ The estimated actual difference was assumed to be 0 because the goal is to achieve same or better pain control as compared to Baseline.

The non-inferiority margin of 1 on a pain scale of 0-10 is equivalent to a non-inferiority margin of 10 on a VAS pain scale of 0-100.

A 33% attrition between enrollment and subject implant is assumed and a 25% attrition between Implant and the 6-Month Visit is assumed. To achieve at least 50 evaluable subjects at the 6-Month Visit, a minimum of 67 subjects are required to be implanted and approximately 100 subjects to be enrolled.

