The 33% attrition between enrollment and subject implant accounts for the subjects who don't meet inclusion and/or exclusion criteria, those who can't follow the weaning process to eliminate systemic opioids, those who don't have a successful IT trial, those who have adverse events that can no longer be followed in the study, withdrawals, and lost-to-follow-up, etc. The attrition between implant and the 6-Month Visit is conservatively set at 25% to potentially account for the subjects who have adverse events that can no longer be followed in the study, withdrawals, are lost-to-follow-up, or subjects who can't be effectively managed on morphine monotherapy.

7. Statistical Methods

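### The targets of 67 implanted and 50 evaluable follow from about 100 enrolled, not from the 93 actually enrolled, and SAP Section 6 still plans for about 100

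*Protocol*

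**What the plan says.** CIP Section 14.1.1 opens with the current numbers, which refer to the 6-Month Visit: "Ninety-three subjects have been enrolled into the study with the intent to achieve approximately 67 implanted subjects and at least 50 evaluable subjects". Its attrition paragraph gives the rates, "A 33% attrition between enrollment and subject implant is assumed and a 25% attrition between Implant and the 6-Month Visit is assumed", and then the history: "Under CIP V2.0, approximately 100 subjects were to be enrolled". It closes by restating the current position, this time without making 50 a minimum: "93 subjects have been enrolled into the study with the intent to achieve approximately 67 implanted subjects and 50 evaluable subjects". The synopsis and Section 6 of the CIP repeat the targets without the rates; the synopsis gives 50 evaluable, while Section 6 makes 50 a minimum. Section 6 adds that the sample size allows for expected attrition and that subjects who exit are not replaced. Section 10.21 repeats both points. Sections 6.1 and 9.2 treat enrolment of 93 as finished.

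SAP Section 6 uses the same two rates but a different enrolment figure: "Approximately 100 subjects will be enrolled into the study to get a minimum of 67 implanted subjects and at least 50 evaluable subjects". It derives the figures backwards from 50 evaluable: "a minimum of 67 subjects are required to be implanted and approximately 100 subjects to be enrolled". SAP Section 3 says that the SAP is based on Version 3 of the CIP, the version that records 93.

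Both documents describe the post-implant rate as cautious (CIP: "The attrition between implant and the 6-Month Visit is conservatively set at 25" percent). Neither says this of the 33% pre-implant rate.

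**The concern.** When enrolment closed at 93, the enrolment figure in the CIP was replaced, but the rates and the targets derived from about 100 were left as they were. Three numbers that should be linked by multiplication no longer are. In the SAP even the enrolment figure was left, so that document announces a future enrolment that its parent CIP reports as complete at a lower number.

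The number 50 carries weight. Both documents base on it the power for the only formal non-inferiority test, the quoted interval widths for Clinical Success, and those for systemic opioid elimination. A reader of the study report will compare the achieved number with 50 and will find that the plan gives no basis for expecting 50 from 93.

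**Working it through.** **Inputs.** Attrition of 33% from enrolment to implant and 25% from implant to the 6-Month Visit (CIP 14.1.1, SAP 6). Enrolled: 93 (CIP 14.1.1) or about 100 (SAP 6). Targets: 67 implanted, 50 evaluable. Power inputs: one-sample t-test, one-sided alpha 0.025, margin 10, SD 19, true difference 0 (CIP 14.1.1, SAP 6). The 25% includes subjects who cannot be managed on morphine monotherapy, so evaluable here corresponds to the per-protocol population.

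**The original plan reproduces.**
- Forward: 100 × (1 − 0.33) = 67.0 implanted; 67 × (1 − 0.25) = 50.25 evaluable.
- Backward: 50 / 0.75 = 66.7, so 67 implanted; 50 / (0.67 × 0.75) = 99.5, so about 100 enrolled.

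**The same rates applied to 93.**
- Implanted: 93 × 0.67 = 62.31, about 62.
- Evaluable: 62.31 × 0.75 = 46.73, about 47.
- Shortfall: about 5 implanted and 3 evaluable.

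**What would have to be true for the targets to hold with 93.**
- 67 implanted: pre-implant attrition of 1 − 67/93 = 28.0% instead of 33%. The stated 25% then gives 67 × 0.75 = 50.25.
- 50 evaluable with 33% lost before implant: post-implant attrition of 1 − 50/62.31 = 19.8% instead of 25%.
- 50 evaluable by any route: overall attrition of 1 − 50/93 = 46.2%, against the assumed 1 − 0.67 × 0.75 = 49.75%.

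**Power for the VAS non-inferiority test** (noncentral t, noncentrality (10/19) × √n).

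| n | Power |
|---|---|
| 50 | 95.4% (the plan states 95%) |
| 47 | 94.2% |
| 46 | 93.7% |

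**Exact (Clopper-Pearson) 95% intervals.**

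| Proportion near | n = 50 | n = 47 |
|---|---|---|
| 70% | 35/50: 55.4 to 82.1, width 26.7 | 33/47: 55.1 to 82.7, width 27.6 |
| 50% | 25/50: 35.5 to 64.5, width 28.9 | 24/47: 36.1 to 65.9, width 29.9 |
| 80% | 40/50: 66.3 to 90.0, width 23.7 | 38/47: 66.7 to 90.9, width 24.1 |

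The n = 50 figures match those printed in CIP 14.3 and 14.4.3 and in SAP 7.9.1.3 and 7.9.4.3.

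**The case against.** The strongest reply is that this is editorial. CIP 14.1.1 sets the rates, the earlier plan of about 100 and the actual 93 next to each other, so a careful reader can see that the rates belong to the 100/67/50 plan. The targets are worded as an intent, and 67 is approximate. When Version 3.0 was written, enrolment was complete and some subjects were already past their 6-Month Visit (CIP 10.10). Part of the attrition had therefore been observed, and applying planning rates to all 93 may misstate what will happen. The post-implant rate is called conservative, so 50 may well be reached. The primary objective has no hypothesis test, enrolment cannot be reopened, and the disposition diagram (SAP 7.1.1) will show the true numbers.

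Much of this stands. The documents do not show that fewer than 50 will be evaluable, and the effect on power and precision is minor. The primary analysis of Clinical Success is also cut at a November 2021 snapshot (SAP 7.1.3, 7.11), so its n may be smaller again. The n = 47 interval widths for Clinical Success apply to the full Per-protocol Analysis Set.

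The reply does not remove the inconsistency. Disclosing the move from 100 to 93 does not rework what follows from it. CIP Section 6 still claims that the size allows for expected attrition, and at the only rates given it does not. The remark about caution covers the 25%, not the 33% behind the 67. In places the documents state the targets as minimums, including 67 implanted in the SAP. If observed attrition supports the targets, neither document says so. The snapshot does not affect the comparison either, because SAP 7.9.1.3 quotes its own interval widths at n = 50. The outdated enrolment figure in SAP 6 has no counter-argument.

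**Conclusion.** The concern holds. At the plan's stated rates, 93 enrolled subjects project to about 62 implanted and 47 evaluable, not 67 and 50. SAP Section 6 contradicts the CIP version on which it is based. The original chain from 100 is correct, and the stated 95% power and interval widths are correct as statements about n = 50; the fault is that 50 is no longer what the inputs deliver.

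The consequence is small: about 1 percentage point of power, and at most about 1 point of interval width. This rests on applying the 33% and 25% rates to all 93 and on the plan's SD of 19 and true difference of 0. The documents give no observed attrition, so the actual evaluable number could fall on either side of 50.

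**What to change.** In SAP Section 6, replace the future-tense enrolment statement with the fact that 93 subjects were enrolled, and identify 100/67/50 as the original planning basis. Then add one of two things:

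- the numbers expected from 93 at the stated rates: about 62 implanted, 47 evaluable and non-inferiority power of about 94%; or
- the observed attrition that supports 67 and 50.

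The text should note that these numbers refer to the per-protocol population at the 6-Month Visit and that the November 2021 snapshot set may be smaller. Align CIP Section 14.1.1, and the minimum of 50 in CIP Section 6, at the next revision. Failing that, give the actual numbers in the study report beside the disposition diagram.

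The cost is one or two sentences in the SAP. Enrolment, analyses, populations and decision rules do not change.
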